### **11.5.8 Cognitive/Clinical Variables**

The following cognitive/clinical assessments will be conducted for this study:

[figure not shown]
- CDR-SB (Clinical Dementia Rating Scale-Sum of Boxes) at visits: Screening (applicable to all subjects except those in Sub-cohort 1.1 and those enrolled prior to Protocol v4.0), Visit 1 (Week 0) (only applicable to sub-cohort 1.1 and to patients enrolled prior to protocol v4.0 being locally approved), Visit 6 (Week 26), Visit 9 (Week 50) and Visit 11 (Week 74). The baseline value is the score obtained at Screening except for subjects of sub-cohort 1.1 and to patients enrolled prior to protocol v4.0 being locally approved for which the baseline value is the score obtained at V1 [Week 0]. For other endpoints, the baseline value is the score obtained at V1 [Week 0].
- RBANS (Repeatable Battery for the Assessment of Neuropsychological Status) at visits: Screening, Visit 1 (Week 0), Visit 6 (Week 26), Visit 9 (Week 50) and Visit 11 (Week 74). Three versions of the scale are used during the study: form A (at V1 and V9), form B (at V6 and V11) and form C (at Screening).
- Mini Mental State Examination (MMSE) at Screening only
- NPI (Neuropsychiatric Inventory Scale) at visits: Visit 1 (Week 0), Visit 6 (Week 26), Visit 9 (Week 50) and Visit 11 (Week 74)
- Columbia-Suicide Severity Rating Scale (C-SSRS) at visits: Screening, Visit 1 (Week 0), Visit 6 (Week 26), Visit 9 (Week 50) and Visit 11 (Week 74)
- MacCAT-CR (MacArthur Competence Assessment Tool for Clinical Research, applicable only to subjects from the Netherlands) at visits: Screening, Visit 5 (Week 24) and Visit 8 (Week 48)

#### 11.5.8.1 CDR-SB

The CDR-SB is a global rating of the function of AD subjects assessed in six categories: memory, orientation, judgement and problem solving, community affairs, home and hobbies and personal care. It is based on a semi-structured interview conducted with the subject and caregiver, by a rater without access to the results of the cognitive tests described above. Each category has scores from 0 (no symptoms) to 3 (severe) and the sum of these items (sum of boxes) may therefore range from 0 to 18 points. The CDR global score is derived from scores of each individual category and will be used as part of the selection criteria (score of 0.5 or 1 at Screening).

Actual values and change from baseline [Week 0 or Screening] will be summarized by Visit (Visit 6 [Week 10], Visit 9 [Week 50] and Visit 11 [Week 74]) and Treatment Group (and overall) for the Intention-to Treat Population [TFL Shell Table 14.3.9].

The CDR-SB data including CDR global score will also be listed for the ITT Population [TFL Shell Listing 16.2.7.10].

Additionally, specific footnote will be included where data on CDR-SB have been collected remotely by telephone interview to specify any details, if needed. Sub-analyses related to the remote mode of administration will not be conducted.

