3.1.1 Cohort 1 with ACI-35.030

For all cohort 1 subjects, the treatment period will last 50 weeks with the treatment/placebo being administered 4 times at respectively 8, 16 and 24-week intervals between each dose. The treatment period will be followed by a 24-week safety follow-up period starting 2 weeks after the last administration until week 74. Subjects who for any reasons have received less than 4 administrations will be followed at least for the same duration after their last administration.

Up to 3 dose levels of ACI-35.030 administered by the intramuscular route will be tested in 3 subcohorts.

Sub-cohort 1.1 (8 subjects):

ACI-35.030 at 300 μ g/dose will be administered to 6 subjects and the placebo will be administered to 2 subjects. The safety and tolerability data after all subjects have received the second injection in sub-cohort 1.1 will permit dose escalation after review by the DSMB.

Sub-cohort 1.2 (8 subjects):

ACI-35.030 at 900 μ g/dose will be administered to 6 subjects and the placebo will be administered to 2 subjects. The safety and tolerability data after all subjects have received the second injection in sub-cohort 1.2 will permit dose escalation after review by the DSMB.

Sub-cohort 1.3 (8 subjects):

ACI-35.030 at 1800 μ g/dose will be administered to 6 subjects and the placebo will be administered to 2 subjects.

For further information on the current study status/progress and relevant safety information, please refer to the IB.

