3.5.2.12 Visit 6 [Week 26]

This visit can take place within a period of up to 2 days.

- AEs
- Concomitant medications (describe new and/or changes from the previous visit)
- Physical and neurological examination
- Vital signs
- Cognition: RBANS (form B)
- Clinical status: CDR, NPI, C-SSRS
- Blood sample collected for:
 - routine hematology and biochemistry evaluation, including CRP
 - antibody response components including for example anti-pTau and anti-Tau IgG and IgM titers
 - Inflammatory cytokines
 - AD biomarker assessment
 - T-Cell profile assessment
 - ANA and anti-dsDNA testing
- Lumbar puncture for cerebrospinal fluid sample (12 mL) for cell count, inflammatory markers and exploratory biomarker testing (note: blood for serum albumin should be taken and measured concomitantly)
- Routine urine evaluation
- Brain MRI
- ECG

Due to the Covid-19 pandemic, local travel restrictions in Finland effective as of 18 March 2020, and the need to preserve the safety of study participants, changes are made to the schedule of visits and procedures of sub-cohort 1.1 subjects:

- Given that the situation is not anticipated to be resolved to allow all procedures to be performed according to the protocol, Visit 6 will not be performed for any sub-cohort 1.1 subjects for whom the planned Visit 6 falls during the at-risk period.
- Instead, a remote visit will be performed in which the subject and caregiver are interviewed by telephone concerning any adverse events or changes in concomitant medications. Where possible, the CDR, NPI and C-SSRS scales will be administered during this interview. The remote visit will be performed at the initially planned Visit 6 date and according to the time-window defined in the Schedule of Assessments, i.e. at week 26 ± 2 days.
- This change is not applicable to the subject who had Visit 5 (week 24) procedures according to the protocol on 18 February 2020.

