5.3.5.1 Cognitive/Clinical variables

The following variables will be included in the analyses:

- 1) Global function (change from baseline in CDR-SB (Clinical Dementia Rating Scale-Sum of Boxes)
- 2) Other cognitive tests (change from baseline in RBANS)
- 3) Behavior (change from baseline in NPI)
- 4) Columbia-Suicide Severity Rating Scale (C-SSRS) scores

Data will be presented per measurement time and dose group.

For endpoint 1), the baseline value is the score obtained at Screening except for subjects of subcohort 1.1 for which the baseline value is the score obtained at V1 [Week 0]. For other endpoints, the baseline value is the score obtained at V1 [Week 0]. Change from baseline [Week 0 or Screening] at Visit 6 [Week 10], Visit 9 [Week 50] and Visit 11 [Week 74] will be summarized per dose group.

For endpoint 4), individual narratives will be presented for all subjects who report serious suicidal intent or any suicidal acts during the study.

Where data on RBANS, CDR-SB and NPI have been collected remotely by telephone interview, at subjects' homes or by videoconference, specific sub-analyses will be conducted in order to explore the potential impact of the remote mode of administration on the related results.

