## 12.0 Changes from the Analysis Planned in the Protocol

Due to the COVID-19 pandemic a notification of an Urgent Safety Measure (USM) for a change to protocol study procedures, effective immediately, was submitted to FIMEA on **01-Apr-2020** and Finnish EC (TUKIJA) on **03-Apr-2020**. A protocol amendment following the USM including the below changes was submitted to FIMEA on **17-Apr-2020** and TUKIJA on **24-Apr-2020**:

- Replacement of Visit 5 (Week 24) and Visit 6 (Week 26) by remote visits in 7 of 8 Sub-cohort 1.1 subjects. As a consequence, the third immunization, as well as procedures and assessments requiring the subjects to travel at Visit 5 (Week 24) and Visit 6 (Week 26) were cancelled.
- Cancellation of the third phone call (P3), usually performed 48-72 hours after the third immunization. This change is impacting 7 of 8 subjects who have not had their immunization at Visit 5 (Week 24) prior to the at-risk period.

Due to the changes presented above IA #2 Sub-cohort 1.1 at Week 50 will be executed as follows:

- Individual data (listings and individual figures) will not be presented for IA #2 Sub-cohort 1.1 Week 50.
- Aggregate data (summary tables and figures) will be provided for all timepoints (up to Week 50) except the timepoints where the visits were missed by 7 of 8 subjects in Sub-cohort 1.1 for which we will have only 1 value (i.e. Visit 5 Week 24 and Visit 6 Week 26).

Footnotes will be included to all outputs affected by the selection criteria as given below:

• Aggregate data outputs: "Note: Aggregate data is provided for all visits except those missed by 7 out of 8 subjects in Sub-cohort 1.1 (Visits 5 and 6)."

In certain cases, where subjects missed any visit or dropped out from the study, IA will be executed as follows:

[figure not shown]
- If there is a risk of unblinding individual data (listings and individual figures) will be presented only up until the missed visit or data for those subjects will not be included.
- Aggregate data (summary tables and figures) will be provided for all timepoints

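### The SAP cancels the remote-rating sub-analyses of CDR-SB, RBANS and NPI that the protocol commits to, gives no reason, and does not list the change in Section 12.0

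*SAP*

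**What the plan says.** **Protocol.** Section 5.3.5.1 (safety) opens its commitment with "Where data on RBANS, CDR-SB and NPI have been collected remotely by telephone interview, at subjects' homes or by videoconference" and continues that "specific sub-analyses will be conducted in order to explore the potential impact of the remote mode of administration on the related results". Section 5.3.7.2 makes the same commitment for the exploratory use of these scales.

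**SAP.** Section 11.5.8.1 (CDR-SB) reverses it: "Sub-analyses related to the remote mode of administration will not be conducted". Sections 11.5.8.2 (RBANS) and 11.5.8.4 (NPI) carry the same sentence. What remains is that a "specific footnote will be included where data on CDR-SB have been collected remotely by telephone interview to specify any details, if needed", with parallel wording for the other two scales. SAP 12.0, the section for changes from the protocol analysis, does not mention the removal.

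**Where remote ratings arise.** SAP 12.0 does record "Replacement of Visit 5 (Week 24) and Visit 6 (Week 26) by remote visits in 7 of 8 Sub-cohort 1.1 subjects". For that remote Visit 6, Protocol 3.5.2.12 says: "Where possible, the CDR, NPI and C-SSRS scales will be administered during this interview". RBANS is not among those scales. Separately, Protocol 3.5.1.1 allows CDR and NPI by telephone or at home for any randomized subject who cannot attend, and prefers telephone. For RBANS it lists only home rating or video supported by a home visit.

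**The concern.** CDR-SB, RBANS and NPI are primary safety and tolerability endpoints (Protocol 2.2.1, SAP 7.1). They depend on an interview or a test session, so a change of mode between baseline and follow-up can shift a score without any change in the subject. The protocol anticipated this and specified a check. The SAP withdraws the check explicitly, so this is not a detail left for later, and a reader who relies on SAP 12.0 would not learn of it.

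The footnote does not fill the gap. It is conditional and limited to telephone. For RBANS it covers a mode that 3.5.1.1 does not list and leaves out the two that it does. Home ratings of CDR and NPI are also uncovered.

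The place where this matters most is Week 26 in sub-cohort 1.1. SAP 8.12 allows telephone visits inside the visit window to be mapped to the scheduled visit and summarized. Baseline in this sub-cohort is Visit 1 for both CDR-SB and NPI (SAP 11.5.8), and 3.5.1.1 applies only after Visit 1. A Week 26 change from baseline there can therefore combine elapsed time with a change of mode in the same subject. (SAP 11.5.8 and Protocol 5.3.5.1 label Visit 6 as Week 10 in places; the schedule of assessments puts it at Week 26.)

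**Working it through.** **1. Commitment against plan.**

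| Item | Protocol | SAP |
|---|---|---|
| CDR-SB, RBANS, NPI mode sub-analyses | To be done (5.3.5.1, 5.3.7.2) | Not to be done (11.5.8.1, 11.5.8.2, 11.5.8.4) |
| Remote modes covered | Telephone, home, video | Telephone only, by footnote |
| Reason for the change | – | None given; absent from 12.0 |

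**2. The plan's own count.** Sub-cohort 1.1 has 8 subjects. One is exempt: "This change is not applicable to the subject who had Visit 5 (week 24) procedures according to the protocol on 18 February 2020". So 8 − 1 = 7, which reproduces the SAP's figure; 7/8 = 87.5%.

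**3. Split by arm.** ACI-35.030 at 300 µg "will be administered to 6 subjects and the placebo will be administered to 2 subjects". The exempt subject's arm is not stated.
- Exempt subject on 300 µg: 5 of 6 active and 2 of 2 placebo had the remote visit.
- Exempt subject on placebo: 6 of 6 active and 1 of 2 placebo.

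The scales were to be given only where possible, so 7 is an upper limit on telephone ratings. Without remote ratings, at most 1 of 8 subjects remains at Week 26, and the 300 µg cell holds 1 value or none.

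**4. How closely mode follows sub-cohort.** Assume 57 subjects: 25 in sub-cohort 1.2 (SAP 6.0) and 8 in each of 1.1, 1.3, 2.1 and 2.2, so 49 lie outside 1.1. Let k be the number of those 49 rated by telephone at Week 26. The documents do not give k, so it is varied. Take all 7 remote subjects in 1.1 as telephone-rated.

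Share of telephone ratings in 1.1 = 7/(7 + k). 
Phi = [7(49 − k) − k] / √[8 × 49 × (7 + k) × (50 − k)].

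| k | Share in 1.1 | Phi |
|---|---|---|
| 0 | 100% | 0.926 |
| 2 | 78% | 0.795 |
| 5 | 58% | 0.659 |
| 7 | 50% | 0.591 |
| 12 | 37% | 0.464 |
| 20 | 26% | 0.325 |

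**5. What a mode comparison could show.** In units of the between-subject SD, assumed equal across groups:
- k = 0: only the 7 against 1 contrast inside 1.1 exists, SE = √(1/7 + 1/1) = 1.07.
- With the other 49 as a second stratum, SE = 1/√[1/(1/7 + 1) + 1/(1/k + 1/(49 − k))]: 0.43 at k = 5 and 0.32 at k = 12.
- Inside 1.1, remote rating coincides with the missed Week 24 injection, so only the second stratum is clean. Alone it gives √(1/5 + 1/44) = 0.47 and √(1/12 + 1/37) = 0.33.

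**6. Does the SAP's COVID-19 sensitivity analysis (11.0) cover this?** It is optional, and its example trigger is more than 10% missed injections, not mode of rating. The 7 missed injections are 7/57 = 12.3% of subjects but 7/(4 × 57) = 7/228 = 3.1% of planned injections, so even the trigger depends on the denominator.

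**The case against.** The case for leaving the SAP alone has substance. These summaries are descriptive, and Protocol 3.5.6 says the study is not powered for comparisons on these scales. If telephone rating was largely confined to sub-cohort 1.1, the promised sub-analysis would have almost nothing to compare. The same 7 subjects did not receive the Week 24 injection, so removing or adjusting for mode would not make the Week 26 300 µg change interpretable. SAP 11.2 already counts subjects with missed visits or alternative contact (Table 14.1.1.3.3). Protocol 3.5.1.1 keeps mode in site source documents or the site file, and nothing shows that it is an eCRF variable, so the work may exceed a table rerun.

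All of this stands as a limit on what the analysis can deliver. None of it is given in the SAP as the reason for removal, and the alternative-contact count does not show mode by scale. If k is small, the reader needs to see that the Week 26 cell rests on remote ratings. If k is moderate, the exploratory look is feasible. Neither case supports an unrecorded deletion.

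A reader might go further and infer that at Week 26 telephone rating is almost completely confounded with the 300 µg dose. The documents do not support that:
- Telephone CDR and NPI are allowed in every sub-cohort, with no counts, so on-site rating at the other doses is not established.
- Seven remote visits are not seven telephone ratings.
- Mode follows the sub-cohort, which includes placebo subjects, rather than the dose.
- RBANS is not a scale of the remote Visit 6, so for those subjects the documents point to missing Week 26 RBANS, not to mode bias.

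**Conclusion.** The point holds as a conflict between the documents: a protocol-specified check on three primary safety scales is cancelled in three SAP sections, without a reason, without an entry in 12.0, and with a substitute that covers one of three remote modes.

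Its clearest local effect is on CDR-SB and NPI at Week 26 in sub-cohort 1.1, at the upper limit of 7 of 8 subjects. In a cohort 1 overall column these would be at most 7 of 41 (8 + 25 + 8), about 17%; any pooled placebo column would include 1 or 2 of them. How far mode and sub-cohort coincide across the trial cannot be settled, because k is not stated; the range in the working runs from near-aliasing at k = 0 to a weak association at k = 20.

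This rests on the assumed total of 57 and, for the upper limits, on all 7 remote visits having produced telephone ratings. No formal inference is affected. The stake is whether readers can interpret the safety summaries and trace the change of plan.

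**What to change.** Reinstate the protocol's sub-analysis in descriptive form:

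1. Tabulate the number of on-site, telephone, home and video ratings by scale, visit and treatment group.
2. Repeat the by-visit change summaries for CDR-SB, RBANS and NPI (Tables 14.3.9, 14.3.10 and 14.3.11.1) without remote ratings.
3. Flag all three remote modes in Listings 16.2.7.8 to 16.2.7.10, in place of the conditional telephone footnote.
4. State that the Week 26 300 µg CDR-SB and NPI changes will not be interpreted as a dose effect, because at most one on-site value remains and the 7 remote subjects also missed the Week 24 injection.
5. Record and justify in SAP 12.0 any departure from the protocol that remains.

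The cost is one count table, three repeated tables and listing flags. The subsets will be small, and some cells will be empty or hold one subject. Mode may have to be confirmed from site source documents if it was not captured in the database.

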#### 11.5.8.2 RBANS

The RBANS is a test designed to measure cognitive decline or improvement in a short series of 12 subtests that measure attention, language, visuospatial/constructional abilities, and immediate and delayed memory. The test yields 5 Index scores and a Total Scale score. Normative information from the test manual is used to calculate the Index and Total scores.

RBANS Total Scale Score and change from baseline will be summarized by Visit (Visit 6 [week 10], Visit 9 [Week 50] and Visit 11 [Week 74]) and Treatment Group (and overall) for the Intention-to Treat Population [TFL Shell Table 14.3.10].

The RBANS data will also be listed for the ITT Population [TFL Shell Listing 16.2.7.9].

Additionally, specific footnote will be included where data on RBANS have been collected remotely by telephone interview to specify any details, if needed. Sub-analyses related to the remote mode of administration will not be conducted.

#### 11.5.8.3 MMSE

The MMSE is a widely used test of overall cognitive function, assessing memory, orientation and praxis in a short series of tests. The score is from 0 to 30 with 30 being the best possible and 0 being the worst possible score. The test will only be performed at the screening visit to confirm subject's eligibility to participate.

The MMSE data will also be listed for the ITT Population [TFL Shell Listing 16.2.7.11].

#### 11.5.8.4 NPI

The NPI is a 12-item scale which assesses domains/behavioral disturbances commonly occurring in dementia subjects. No score will be calculated if there is missing data in any item scale. Twelve domains/behavioral areas are included in the NPI: delusions, hallucinations, agitation/aggression, depression/dysphoria, anxiety, elation/euphoria, apathy/indifference, disinhibition, irritability/lability, aberrant motor behavior, night-time behaviors, and appetite/eating changes. Through a structured interview with the caregiver, each of these 12 domains will be assessed. For each behavior that has not occurred a frequency of 0 will be recorded. For each behavior that is determined to have occurred, the frequency (1: Occasionally, 2: Often, 3: Frequently, 4: Very Frequently) and severity (1: Mild, 2: Moderate, 3: Marked) will be determined. The frequency and severity will be multiplied together to provide a total score. The total NPI score is calculated by summing across all 12 domains/behaviors generating a score which ranges from 0 (no behaviors present) -144 [all behaviors present with greatest frequency (4: Very Frequently) and greatest severity (3: Marked), i.e. 12x4x3]; a higher score indicates more severe psychopathology. Additionally, the caregiver distress for each domain/behavior will be assessed (0: Not at all, 1: Minimally, 2: Mildly, 3: Moderately, 4: Severely, 5: Very severely or extremely). The NPI Total Distress Score is calculated by adding the individual distress scores for the individual domains/behaviors. The NPI Total Distress Score will range from 0 (0: Not at all recorded for each domain/behavior) to 60 (5: Very severely or extremely recorded for each domain/behavior, i.e. 12x5); a higher score indicates greater caregiver distress.

The NPI Total Score and change from baseline will be summarized by Visit (Visit 6 [Week 10], Visit 9 [Week 50] and Visit 11 [Week 74]) and Treatment Group (and overall) for the Intention-to Treat Population [TFL Shell Table 14.3.11.1].

The NPI Total Distress Score and change from baseline will be summarized by Visit (Visit 6 [Week 10], Visit 9 [Week 50] and Visit 11 [Week 74]) and Treatment Group (and overall) for the Intention-to Treat Population [TFL Shell Table 14.3.11.2].

The NPI data will be also listed for the Intention-to Treat Population [TFL Shell Listing 16.2.7.8].

Additionally, specific footnote will be included where data on NPI have been collected remotely by telephone interview to specify any details, if needed. Sub-analyses related to the remote mode of administration will not be conducted.

### 11.5.8.5 C-SSRS

Recent guidance from the FDA has indicated the importance of collecting data on potential induction of suicidal behavior with all new agents acting on the central nervous system. Although no such effects are anticipated with the study vaccines investigated, this will be directly evaluated by collecting the C-SSRS, at the visits indicated above, during the study. Questions related to suicidal behavior or ideation are directly asked by the rater to the subject. The C-SSRS has a "Baseline Version" which will be completed at the Screening visit and a "Since Last Visit Version" that will be completed at all other study visits.

The frequency of suicidal ideation and whether or not subjects exhibited suicidal behavior will be summarized by Treatment Group (and overall) [TFL Shell Table 14.3.12].

[figure not shown]
The C-SSRS data will be also listed for the Intention-to Treat Population [**TFL Shell Listing 16.2.7.12**] individual narratives will be presented for all subjects who report serious suicidal intent or any suicidal acts during the study.

## 11.5.8.6 MacCAT-CR

In the Netherlands, the subject's decisional capacity will be assessed by using the MacArthur Competence Assessment Tool for Clinical Research (MacCAT-CR). The MacCAT-CR assesses the subject capacities to consent to research participation (Appelbaum and Grisso, 2001). It is a 21-item structured interview with four subscales assessing the following four main dimensions of decision making: understanding, appreciation, reasoning, and expressing a choice. Questions are tailored to the research context defined in this protocol. The determination that the subject is able to give informed consent and is able to maintain his/her decisional capabilities during the study will be based on the subject's responses to the questions in conjunction with the Investigator's clinical judgement. The rater must be an investigator or delegate adequately trained.

The MacCAT-CR interview will be performed at study start prior to signing the informed consent form and subsequently at V5 and V8. In case it is determined that the subject is no longer able to maintain his/her decisional capacity, participation should be discontinued.

For the MacCAT-CR assessment, the baseline value is the score obtained at Screening. The proportion of subjects in the Netherlands (please refer to Protocol V7.0 / 22-Oct-2021) who are maintaining their decision-making capacity at Visit 5 [Week 24] and Visit 8 [Week 48] using the MacCAT-CR assessment will also be presented per dose group [TFL Shell Table 14.3.13]. The details will be listed [TFL Shell Listing 16.1.7].

